Appendix 2: Usability Questionnaire

Name of staff member: _____

Position (i.e., nurse, physician, etc.): _____

How would you rank the following tasks on a scale from 1 to 5?

(Circle the response that best represents your opinion)

1. How would you rate the difficulty level of priming and loading the smART System?

1	2	3	4	5
Very Hard	Hard	Average	Easy	Very Easy

2. Over all, how would you rate the operation of the console unit?

1	2	3	4	5
Very Hard	Hard	Average	Easy	Very Easy

3. Over all, how easy was it for you to operate the system?

1	2	3	4	5
Very Hard	Hard	Average	Easy	Very Easy

4. How useful was the system feedback during feeding tube placement?

1	2	3	4	5
Very Bad	Bad	Average	Good	Very Good

5. If an error message occurred during use, how easily was the issue resolved?

1	2	3	4	5
Very Hard	Hard	Average	Easy	Very Easy

6. How would you rate the smART System with respect to "user friendliness"?

1	2	3	4	5
Not Friendly	Somewhat Friendly	Average	Friendly	Very Friendly

SUBJECT: Functionality and Accuracy of the smART System in Real-Life ICU Settings

Number: CLT3_SY_P001

Revision 08

Page 37 of 38

7. How satisfied were you with the display and prompts provided by the console?

1 Very Unsatisfied	2 Unsatisfied	3 Average	4 Satisfied	5 Very Satisfied
------------------------------	-------------------------	---------------------	-----------------------	----------------------------

8. In your opinion based on what you experienced during the study, would you (as the caregiver) how would you rate having the device routinely used in your establishment?

1 Very unhelpful	2 Unhelpful	3 Average	4 Beneficial	5 Very beneficial
----------------------------	-----------------------	---------------------	------------------------	-----------------------------

9. How satisfied are you with the time it takes to learn how to operate the system (i.e., learning curve)?

1 Very Unsatisfied	2 Unsatisfied	3 Average	4 Satisfied	5 Very Satisfied
------------------------------	-------------------------	---------------------	-----------------------	----------------------------

10. How easy was it to connect between hospital accessories (feeding bag, IV pole) and smART system?

[figure not shown]
1 Very Hard	2 Hard	3 Average	4 Easy	5 Very Easy
-----------------------	------------------	---------------------	------------------	-----------------------

11. How would you rate the stability of the smART console with respect to the connection to hospital IV pole?

1 Very Unstable	2 Unstable	3 Average	4 stable	5 Very Stable
---------------------------	----------------------	---------------------	--------------------	-------------------------

12. How would you rate the smART console buttons with respect to sensitivity of presses and sufficient illumination?

1 Very Bad	2 Bad	3 Average	4 Good	5 Very Good
----------------------	-----------------	---------------------	------------------	-----------------------

PATIENT SAFETY THROUGH TECHNOLOGY

Date issued:
05 Dec2018

SUBJECT: Functionality and Accuracy of the smART System in Real-Life ICU Settings

Number: CLT3_SY_P001

Revision 08

Page 38 of 38

13. In your opinion based on your familiarity with other various devices in ICU, how would you rate the device's buzzer and alert volume?

1

2

3

4

5

Very Bad

Bad

Average

Good

Very Good

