4.2 Secondary Endpoints

- Ease of use of the system and the user interface by subjective questionnaire of staff
- Recording of impedance detected by the system and correlation to patient positioning
- Quantification of the amount of discarded nutritional supplement by implementing GRV test as needed and according to hospital procedures
- Reduction of aspiration of gastric contents percentage compared to standard feeding (as reported in literature).
- Correlation between patient clinical information and the occurrence of reflux and sensors data.

5 Study Conduct & Population

This study will be performed in accordance with the design and specific provisions of this protocol, in accordance with the ethical principles that have their origin in the Declaration of Helsinki, that are consistent with Good Clinical Practice (GCP), Title 21 of the Code of Federal Regulations (21 CFR), part 812 (Investigational Device Exemptions), and the applicable regulatory requirements.

SUBJECT: Functionality and Accuracy of the smART System in Real-Life ICU Settings

Number: CLT3_SY_P001

Revision 08

Page 17 of 38

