Every smART feeding tube removal should be documented in the CRF and the relevant device information (i.e., serial number) should be recorded. If a smART tube is replaced by a different smART tube, the reason for replacement should be documented and the serial number of the new device being used should be recorded.

- **Endoscopy/esophageal imaging**

One third of the study population will undergo endoscopy to evaluate potential trauma to the esophagus as a result of balloon inflation.

Endoscopy will be indicated for those patients who:

- Have been enrolled in the study for a duration of more than 5 days;

Or,

- Had noticeable blood residue on the feeding tube following tube removal.

PATIENT SAFETY THROUGH TECHNOLOGY

Date issued:
05 Dec2018

SUBJECT: Functionality and Accuracy of the smART System in Real-Life ICU Settings

Number: CLT3_SY_P001

Revision 08

Page 21 of 38

If by the time patient number 13 is enrolled, no endoscopies have been performed, the remaining 7 patients will undergo endoscopy for local evaluation of trauma in the area of the esophagus where the balloon is inflated.

Every effort will be made to obtain at least 7 patients with endoscopic assessment.

Procedure - Following tube removal (within 5 hrs.) patients eligible for endoscopy (based on the above definition) shall undergo an endoscopic procedure to evaluate the balloon inflation site. Specifically, any noticeable trauma to the esophagus shall be recorded in the relevant CRF pages (e.g., adverse event form).

- Aspiration of gastric contents recording

Local site procedure for tracheal suction should be followed as needed and according to hospital procedures. Once every eight hours a sample of at least 2 cc should be instilled in a LUKI trap. The sample should be appropriately labeled and recorded by the medical staff in the bed side CRF log (Pepsin Test). The sample should be kept frozen until transportation to the lab.

- Used/Unused Devices

Used devices will be returned back to the bag in which they were provided in by the sponsor. All the bags will be collected by the sponsor, and accountability logs will be updated accordingly.

All unused devices and study materials will be collected by the sponsor at the end of the study.

- Staff Questionnaires:

At the end of the study, staff will be required to complete a usability questionnaire assessing the ease of use and functionality of the device (refer to Appendix 2).

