9.2 Statistical Analysis

The analyses will be carried out according to intention to treat as well as per protocol. Categorical parameters will be summarized by frequencies and percentage, while quantitative variables will be summarized by mean, median, standard deviation and range. In particular, the following tests according to the parameter type will be performed:

- Continuous parameters will be presented by the estimated value and calculation of 95% confidence intervals.
- Nominal categorical parameters will be analyzed by Fisher exact test/ chi-square tests (in case of low observed frequencies).
- Ordinal categorical parameters will be analyzed by Wilcoxon rank sum test.

[figure not shown]
Alternatively, if data will support the assumption of normality:

- Comparison between continuous parameters will be analyzed by the appropriate Student T-test.

10 Data Management

Data from each subject will be recorded by the hospital (as needed and according to hospital procedures) and will transmitted manually to CRFs supplied by the sponsor. Quality check for errors and omissions will be performed to ensure the accuracy of the entered data. Information to be transmitted from the hospital source to the company CRF includes (but is not limited to): patient position changes, patient feedings, GRV (gastric residual volume), vital signs and medication record, etc.

The source data should be completed during the study by qualified personnel. All data must be filled out using ball pens (not pencils), accurately and promptly following each relevant step of the study. The CRF should be completed in full, i.e., no fields should be left blank once the subject has completed the study. CRFs entries corrections must be made only by lining out (single line) incorrect data and writing in the revisions. All corrections must be initialed and dated by the individual performing/recording the correction on the day of correction. If the reason for the change is not obvious, an explanation for the change should be recorded and attached to the CRF. Blacking out or using correction fluid or an eraser is not allowed to correct or eliminate data. The investigator

SUBJECT: Functionality and Accuracy of the smART System in Real-Life ICU Settings

Number: CLT3_SY_P001

Revision 08

Page 30 of 38

must review the CRFs for completeness and accuracy and must sign/date the forms where indicated. Signature stamps or substitutes are not acceptable.

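### Two of the 13 usability items are hard to interpret as printed: item 5 has no answer for staff who saw no error, and item 6 has unbalanced anchors

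*Combined protocol and SAP*

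**What the plan says.** Section 4.2 lists as a secondary endpoint "Ease of use of the system and the user interface by subjective questionnaire of staff". Staff feedback on use and usability is also objective 4 in Section 3. Appendix 2 is the only instrument named for it.

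Under Staff Questionnaires, Section 6.2.3 says that at the end of the study "staff will be required to complete a usability questionnaire assessing the ease of use and functionality of the device". The form's general instruction is "Circle the response that best represents your opinion", on a scale of 1 to 5.

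- **Item 5** reads "If an error message occurred during use, how easily was the issue resolved". The printed answers are *Very Hard*, *Hard*, *Average*, *Easy* and *Very Easy*. There is no not-applicable option and no skip instruction.
- **Item 6** asks about user friendliness. Its answers are *Not Friendly* (1), *Somewhat Friendly* (2), *Average* (3), *Friendly* (4) and *Very Friendly* (5).

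Section 9.1 says the results will be evaluated descriptively. Section 9.2 summarises categorical parameters by frequency and percentage, and names a rank sum test for ordinal ones. It gives no questionnaire score, no threshold and no rule for a missing item. The number of staff respondents is not stated.

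**The concern.** Item 5 is the only item on recovering from an error, and its wording applies only to staff who met one. The form cannot record that a respondent did not. Two kinds of answer are therefore ambiguous. A circled number may be a true rating or a guess, and a blank may mean no error or an overlooked item. The reader of the results cannot tell how many people the item 5 percentages describe.

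Item 6 has a different fault. Its label at 2, "Somewhat Friendly", is mildly favourable in words but sits below the midpoint in score. A score of 2 on item 6 does not mean what a 2 means elsewhere on the form.

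At stake is whether these two items can be interpreted. No success criterion, comparison or safety conclusion depends on them.

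**Working it through.** The plan gives no figure for this endpoint, so there is nothing to reproduce. The check compares the items and then illustrates the possible size.

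**1. Anchors across the form.** Items 1 to 5 and 7 to 13 (12 items) each have two unfavourable labels, *Average*, and two favourable labels. Item 6 has one unfavourable label, *Average*, and three labels that express some friendliness, one of them placed below *Average*. It is the only item that departs from the pattern.

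**2. Share of the form affected.** 2/13 = 15.4%; item 5 alone is 1/13 = 7.7%.

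**3. Item 5 when staff without an error circle a number.** Let f be the share of respondents who saw no error, m the rating given by those who did, and c the number circled by the rest. The observed mean is m(1 − f) + cf. None of these values is in the documents; all are assumptions.

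| m | c | Formula | f = 0.1 | f = 0.4 | f = 0.8 |
|---|---|---|---|---|---|
| 2 | 3 | 2 + f | 2.1 | 2.4 | 2.8 |
| 4 | 3 | 4 − f | 3.9 | 3.6 | 3.2 |

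The first row flatters the device and the second does the reverse, so the sign is not fixed. The same holds for percentages, the summary that Section 9.2 gives for categorical parameters. If everyone who met an error circled 2 and f = 0.4 of respondents circled 3, the share answering *Hard* would read 1 − 0.4 = 60% instead of 100%.

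**4. Item 5 when staff without an error leave it blank.** With b blanks, the number who saw no error and left the item blank lies anywhere from 0 to b. The form cannot narrow that range.

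**5. Item 6.** On the pattern of the other items, a mildly favourable user scores 4. Going by the words on item 6, that user may circle 2, which is 2 points lower. A mildly unfavourable user would score 2 elsewhere but finds no such label here, and may move to 1 or to 3. Displacement in either direction is plausible.

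**6. Ceiling on a total score, if one were used.** The documents define none, so assume an unweighted 13-item mean. Including an item 5 value x that should have been omitted changes a respondent's mean by (x − mean of the other 12)/13. On a 1 to 5 scale this is at most 4/13 = 0.31. Item 6 adds 1/13 = 0.08 for one point of displacement, or 2/13 = 0.15 for two. Together the ceiling is 5/13 = 0.38 or 6/13 = 0.46. These are limits, not estimates.

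**The case against.** The strongest case for the form is that item 5 begins with a condition, so a sensible respondent with no error will skip it, and nothing forbids that. A reader might infer that staff are forced to rate, because "staff will be required to complete a usability questionnaire" and because Section 10 says "no fields should be left blank once the subject has completed the study". The documents do not support this. The first requires the questionnaire, not every item. The second is a rule about the CRF, and no text makes the questionnaire part of the CRF. This part of the objection stands, but skipping still leaves the blank ambiguous.

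A second defence is that the console keeps an event log (Section 1.2), from which errors could be counted. That log is kept per patient, and nothing says that it links an error message to the staff member who later fills in the form.

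Third, a reader might infer that item 6 flatters the device. That does not follow: a favourable label scored at 2 can also pull results down. The ordered numerals and the *Average* label at 3 limit misreading, but do not restore comparability with the other items.

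Fourth, a reader might infer that the field "Name of staff member" discourages criticism because the sponsor collects study materials. That collection sentence stands under Used/Unused Devices in Section 6.2.3 and does not mention completed questionnaires. Section 10 has the investigator retain the originals of CRFs, consent forms and study data. A staff code would be a preference, not the correction of a fault.

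**Conclusion.** The point holds as a minor one. Item 5 offers no valid answer to staff who saw no error, so its ratings, its blanks and its denominator cannot be interpreted with confidence. Item 6 cannot be read on the same footing as the other 12 items. Both facts are visible on the printed form and need no assumption. The size and sign of any bias are not known, because the documents give neither the share of staff without an error nor how they would respond.

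A reader might go further and conclude that the ease-of-use endpoint as a whole is distorted. The documents do not support that. Two of 13 items are affected, and items 1, 2, 3 and 10 ask about ease or difficulty of use directly with balanced anchors. The analysis is descriptive and no composite is defined. If items are reported one by one, the problem stays within items 5 and 6.

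**What to change.** - **Item 5:** add the answer *No error message occurred*. Report the rating frequencies only among staff who met an error, and state that denominator beside the number who chose the new answer and the number left blank.
- **Item 6:** change the anchors to *Very Unfriendly*, *Unfriendly*, *Average*, *Friendly*, *Very Friendly*, to match the rest of the form.
- **Section 9.2:** add a sentence saying that the questionnaire is summarised item by item.

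The cost is a small revision of a protocol appendix. Section 11 requires written confirmation of a modification before it is implemented. Section 12 requires prior IRB approval of amendments, except to remove an immediate hazard or where the change is only logistical or administrative. Since this alters the response scale of an endpoint instrument, the sponsor should settle with the IRB whether that exception applies. The change should come before any form is filled in, because whether a respondent met an error cannot be reliably recovered afterwards.
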